12.4 Final Analysis

The database will be locked prior to the final analysis (FA) which will be conducted when all randomized subjects have reached Week 56 or terminated early. As described in [Section 12.3](#), all the efficacy endpoints will be tested in a hierarchical order, at the highest tolerated dose of IMR-687 vs placebo. If all the efficacy comparisons are successful, testing of the IMR-687 pooled dose vs. placebo, and of lower dose vs. placebo will be performed. Propagated alpha from the primary efficacy analysis at the IA will be used in the FA to maintain an overall type I error rate of 5% for 2-sided testing. After the first instance of a failure to reject the null hypothesis, p-values from all remaining comparisons will still be reported, but deemed nominal. The hierarchical order of testing of primary, key secondary and other secondary endpoints is:

1. Annualized rate of VOCs
2. Time to first VOC
3. HbF responder rate at Week 24
4. Proportion of VOC-free subjects
5. Annualized rate of VOC-related hospitalization
6. Annualized rate of days hospitalized for VOC-related hospitalizations
7. Time to second VOC
8. Change from baseline in key biomarkers of RBC hemolysis (indirect bilirubin and % reticulocytes) at Week 24 and Week 52
9. HbF responder rate at Week 52
10. Change from baseline in HbF (%) and F-cells (%) at Week 24 and Week 52
11. Hb responder rates at Week 24 and Week 52
12. Change from baseline in total Hb (g/dL) at Week 24 and Week 52
13. Change from baseline in other biomarkers of RBC hemolysis (absolute reticulocytes and lactate dehydrogenase [LDH]) at Week 24 and Week 52
14. Change from baseline in biomarkers of adhesion such as soluble E-selectin (E-sel), P-selectin (P-sel), intercellular adhesion molecule 1 (ICAM-1), and vascular cell adhesion molecule 1 (VCAM-1) at Week 24 and Week 52
15. Change from baseline in biomarkers of inflammation such as high-sensitivity C-reactive protein (hsCRP) and myeloperoxidase (MPO) at Week 24 and Week 52
16. Change from baseline in biomarkers of cardiac stress such as N-terminal prohormone of brain natriuretic peptide (NT-proBNP) at Week 24 and Week 52
17. Change from baseline in RBC indices, such as mean corpuscular volume (MCV) at Week 24 and Week 52
18. Change from baseline in each measured subdomain of ASCQ-Me questionnaire at Week 24 and Week 52
19. Change from baseline in total preference score and individual domain scores of PROPr questionnaire at Week 24 and Week 52
20. Change from baseline in overall score of the Sickle Cell Self-Efficacy Scale (SCSES) at Week 24 and Week 52

Some of the other secondary endpoints listed above include multiple endpoints at multiple time points. In terms of the hierarchical order of the testing, the endpoint listed earlier will be tested first for the earlier time points, before the endpoint listed later. For example, for point #9, it will be considered as 4 endpoints in the order of:

- Change from baseline in HbF (%) at Week 24
- Change from baseline in F-cells (%) at Week 24
- Change from baseline in HbF (%) at Week 52
- Change from baseline in F-cells (%) at Week 52

For points #18 and #19, the individual domains are in the order as listed in [Section 13.5.4](#).

12.5 Data Monitoring Committee

The specific activities of the DMC will be governed by a charter which will define the DMC's membership, meeting frequency, procedures/conduct, and requirements for reporting its observations to the sponsor.

To ensure safety oversight throughout the trial, the DMC will review safety and preliminary efficacy data and provide recommendations to the Sponsor as described below.

The DMC will convene at the following times and for the following activities during the trial:

- Review safety data for at least 5 subjects who received IMR-687 at the lower dose and make recommendation as to the inclusion of the higher dose. This potential study adjustment makes the design adaptive.
- Review safety data to confirm acceptable safety and tolerability of the higher dose of IMR-687 and make recommendation as to whether the dose levels could be modified.
- Review safety data on a periodic basis.
- At any time during the trial—upon request by the Sponsor, medical monitor, or DMC—should a concern arise from emerging safety data for which DMC review and assessment is desired. This includes the emergence of a frequency or pattern of AEs or SAEs that suggests an unexpected or otherwise concerning safety signal. At any time, the DMC may recommend stopping a dose arm or the study for safety concerns.

The DMC may review the following subject data, depending on the scope of the meeting, and may recommend that the study continues as planned, that the protocol be modified, that a dose level should be stopped (which will inform the highest tolerated dose for analyses), or that the study terminate for safety concerns:

- Unblinded safety, PK, and preliminary efficacy/PD data, which may include TEAEs, SAEs, PK data, clinical laboratory test results, vital signs, and other relevant data for all subjects randomized.
- The DMC chairperson will receive copies of all SAE reports for ongoing review during the study. The DMC chairperson may forward an SAE report to the full DMC if he/she feels that their immediate input on, or awareness of, the SAE would be helpful.
- Additional unblinded summary reports (at group level) for IA and FA.

All assessments, decisions, and recommendations by the DMC will be documented in writing as noted in the DMC charter and prior to any resultant changes to the study unless their immediate implementation is considered necessary for subject safety.

13.0 Statistical Methods

All statistical analyses will be conducted using SAS Version 9.4 or other validated software.

Descriptive summary statistics will be provided for demographics, disposition, and treatment exposure. The number and percentage of subjects who discontinue from the study, along with reasons for discontinuation will be tabulated.

Continuous data will be summarized using descriptive statistics (number of subjects, mean, SD, median, first quartile (Q1), third quartile (Q3), minimum, and maximum, as well as geometric statistics as applicable). Counts and percentages will be used for summarizing categorical (discrete) data. For summaries of categorical variables, counts and percentages are based on the number of subjects in the analysis set unless otherwise specified.

All statistical tests and resulting p-values will be reported as 2-sided. Two-sided confidence intervals, when presented, will generally be constructed at the 95% level. P-values should be presented to 4 decimal places, with values less than 0.0001 presented as <0.0001. Multiplicity adjustment will be used for the IA and FA using the Lan-DeMets alpha spending function, as specified in [Sections 12.3](#) and [Section 12.4](#).

In general, means and medians will be presented to 1 or more decimal places than the recorded data. The SDs will be presented to 2 more decimal places than the recorded data. Confidence intervals about a parameter estimate will be presented using the same number of decimal places as the parameter estimate. Percentages will be presented to 1 decimal place.

A month is operationally defined to be 30.4375 days. A year is operationally defined to be 365.25 days.

If a subject was assigned the wrong stratum at randomization, their stratum based on the randomization system will be used for the statistical analyses. Analyses may be repeated using actual stratum if mis-randomization occurs in more than 10% of randomized subjects.

Where specified, there will be pair-wise comparisons between IMR-687 higher dose vs placebo, IMR-687 pooled dose vs. placebo, and IMR-687 lower dose vs placebo. Of note, by study design, subjects will be randomly assigned in a 2:1 ratio to receive either IMR-687 lower dose or placebo respectively at phase one of the trial. When the DMC recommends inclusion of the higher dose, randomization will then proceed in a 1:2:1 ratio (IMR-687 lower dose, IMR-687 higher dose, or placebo), as the second phase. The placebo and lower dose from the two phases will be analyzed together without any adjustment in the statistical analysis.

The following labels will be displayed in tabulations, unless otherwise specified:

Table 6 Treatment Groups in Tabulations

| Placebo | IMR-687 200/300 mg | IMR-687 300/400 mg | IMR-687 Pooled Dose | Total |
|---------|-----------------------|-----------------------|------------------------|-------|
|---------|-----------------------|-----------------------|------------------------|-------|

The total column will only be included in the concomitant medication summaries and in the summaries pertaining to information collected before the treatment started, such as demographic, baseline and disease characteristics and prior medications.

In general, all clinical data collected from CRF, or laboratory will be stored in SDTM datasets in STDM structure and presented in subject listings.

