Initially, subjects will be randomly assigned in a 2:1 ratio to receive either IMR-687 lower dose or placebo. Prior to the introduction of IMR-687 higher dose, the Data Monitoring Committee (DMC) will review safety data for at least 5 subjects who received IMR-687. If the DMC recommends inclusion of the higher dose, randomization will then proceed in a 1:2:1 ratio (IMR-687 lower dose, IMR-687 higher dose, or placebo). During study conduct under Protocol Version 3.0, the DMC approved opening of enrollment to the higher dose IMR-687 group, enrollment to the higher dose went into effect on 12 March 2021.

[figure not shown]
Subjects may or may not be concomitantly receiving a stable dose of hydroxyurea (HU) according to the subject's established treatment plan. Randomization will be stratified by use of HU (yes vs. no) and by region (North America/Europe vs. Africa/Middle East).

Subjects will be directed to take study drug (either IMR-687 or placebo) with food, but if a subject does not do so, it will not be considered a protocol deviation.

An interim analysis (IA) will be conducted when all subjects have completed study assessments (including VOC incidence) at Week 24 or terminated the study early. The IA will be a partial unblinding event with corresponding alpha spending strategies to manage Type 1 error.

A final analysis (FA) will be conducted at study completion (i.e., when all subjects have reached Week 56 or terminated early), following database lock and unblinding. Alpha available at the final analysis will be propagated based on the alpha spent from the IA.

Figure 1: Overview of Study Design and Dose Groups

Abbreviation: DMC = data monitoring committee.

* Prior to the introduction of IMR-687 higher dose, the DMC will review safety data for at least 5 subjects who received IMR-687. If the DMC recommends inclusion of the higher dose, randomization across 3 dose groups will then proceed as shown.

During study conduct under Protocol Version 3.0, the DMC approved the opening of enrollment in the higher dose IMR-687 group, which went into effect on 12 March 2021.

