8.1 Sample Size and Power Considerations

8.1.1 Sample Size Determination

The sample size of this study was originally determined based on HbF responder rate as the primary endpoint:

Assuming a 5% HbF response rate for placebo, the study having approximately 31 placebo and 49 higher dose subjects would have > 85% power to detect a targeted difference of 30%, using a Chi-square test for comparison of proportions (with continuity-correction) and a two-sided alpha of 0.050. The assumed responder rate for placebo (5%) and highest tolerated dose subjects (>35%) includes the dropout subjects (regarded as are non-responders at Week 24).

Based on FDA feedback a new primary endpoint was adopted with a corresponding change in statistical methodology as specified in Section 8.1.2 below.

As of completion of this SAP, enrollment was completed in the ongoing study, with a total of 115 subjects randomized between August 2020 and August 2021. Out of the 115 subjects, the first 17 subjects were randomized in a 2:1 ratio to Lower Dose: Placebo, and the remaining 98 subjects proceeded with randomization in a 1:2:1 ratio for Lower Dose: Higher Dose: Placebo.

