8.1.2 Power Estimation

Annualized rate of VOCs was changed from a key secondary endpoint in Protocol 4.0/4.1 (April 2021) to the primary efficacy endpoint in this SAP and in Protocol Amendment 5.0/5.1 (February 2022). The power calculation below was based on the projection that there will be approximately 49 randomized subjects in higher dose, 35 subjects in lower dose and 31 subjects in placebo group.

Assuming that the actual data distribution is normal when the significance level (alpha) of the test is 0.050, the standard deviation is 2.7 in both groups, and there are no dropouts, there will be 88% power to detect a difference between the medians of 5.0 and 3.0 for the placebo and the IMR-687 highest tolerated dose groups, respectively (i.e., a 40% difference), using a two-sided Wilcoxon Rank-Sum test ([Table 1](#)). Assuming a 25% dropout rate, the power will be 78%.

Table 1 Power Estimation

| Scenarios | N for IMR-687 Highest Tolerated Dose | N for Placebo | Significance Level (two-sided alpha) | Standard Deviation | Difference | Power |
|------------------------|--------------------------------------|---------------|--------------------------------------|--------------------|------------|-------|
| No Dropout | 49 | 31 | 0.05 | 2.7 | 40% | 88% |
| With 25% Dropout Rate* | 37 | 24 | 0.05 | 2.7 | 40% | 78% |

* estimated based on Ataga et al.

The power calculation for the Annualized rate of VOCs was carried out in PASS Version 2020 v20.0.3. See [Appendix 7](#) for details.

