12.0 Overview of Planned Analyses

This section summarizes the planned analyses for efficacy, PD, PK and safety for the interim analysis (IA) and final analysis (FA). The statistical analyses, which will be performed on locked and cleaned data extracts, will include all data through protocol-specified analysis time points. The data cut-off for the IA are specified below. The DMC may recommend the discontinuation of a dose arm, due to safety, which will inform the highest tolerated dose. Selected personnel involved in the analysis and review of unblinded data for the IA will abstain from attending study conduct and operational meetings after the data has been unblinded for any reason. Detailed statistical methods are defined in [Section 13.0](#).

An IA will be performed after all subjects have reached Week 24 or terminated early. The FA will be performed after all subjects have completed the study. The critical significance levels for the IA and FA to maintain an overall two-sided type I error rate of 5% will be based on an O'Brien-Fleming boundary, calculated from a Lan-DeMets alpha spending function, based on the number of highest tolerated dose and placebo subjects used in the primary efficacy analysis in the ITT analysis set.

A summary of planned analysis for IA/FA are summarized in [Table 4](#) below.

Table 4 Planned Analyses for IA and FA

| | IA | FA |
|--|--|--|
| Disposition, Baseline and Disease Characteristics | Yes | Yes |
| Exposure | Yes | Yes |
| Concomitant and Prior Medications | | Yes |
| Primary Efficacy: Annualized Rate of VOCs | Yes, with Alpha spending - fixed sequence design [a] | Yes, with propagated Alpha from IA [a] |
| Key Secondary Efficacy: Time to first VOC and HbF Responder rate at Week 24 | Yes [b] | Yes [b] |
| Other Secondary Efficacy: Biomarkers and Specialty Hematology parameters | | Yes |
| Other Secondary Efficacy (Annualized rate of VOC-related hospitalizations, etc.) | | Yes |
| Other Secondary Efficacy: PROs (ASCQ-Me, PROPr, SCSES) | | Yes |
| Exploratory Efficacy | | Yes |
| Subgroup Analysis | | Yes |
| Safety (AEs, Laboratory, Vital Signs, ECGs, etc.) | Yes, selected outputs only | Yes |
| PK | Yes, selected outputs for plasma concentration only | Yes |

[a] Two-sided alpha spending at IA for primary efficacy analysis is 0.002. Propagated Alpha of 0.0494 is to be spent at FA.

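### Placebo and lower-dose subjects from the 2:1 and 1:2:1 phases are pooled with no allowance for phase, so about 6 of the 31 placebo controls in the primary comparison are non-concurrent, and no planned analysis checks this

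*SAP*

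**What the plan says.** Randomisation had two phases. SAP Section 8.1.1 describes the first one: "the first 17 subjects were randomized in a 2:1 ratio to Lower Dose: Placebo". The other 98 were then allocated 1:2:1 across lower dose, higher dose and placebo. The same section gives the overall count and period, "with a total of 115 subjects randomized between August 2020 and August 2021". SAP Section 8.0 dates the switch: "enrollment to the higher dose went into effect on 12 March 2021". For the analysis, SAP Section 13.0 says: "The placebo and lower dose from the two phases will be analyzed together without any adjustment in the statistical analysis".

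The power calculation in SAP Section 8.1.2 assumes "approximately 49 randomized subjects in higher dose, 35 subjects in lower dose and 31 subjects in placebo group", so its placebo count includes the early subjects.

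The primary test (SAP 13.5.2 and 13.5.2.2, SAS template in Appendix 6) stratifies by region and HU use only. None of the sensitivity analyses in 13.5.2.4 and none of the subgroups in 13.5.6 uses phase or is limited to concurrent placebo. Protocol Sections 7.1.2 and 10.1 describe the change of ratio but give no analysis for it. The pooled-dose and lower-dose comparisons with placebo are formal steps in the testing hierarchy (SAP 12.4, 13.5.2.2).

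**The concern.** Randomisation protects the comparison of higher dose with placebo only among subjects who could have been assigned to either arm. The placebo subjects from the 2:1 phase could not have been. If early subjects differ in VOC rate, in how VOCs are recorded or in case mix, part of that difference appears as a treatment effect.

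The other two comparisons have a related problem. Both arms recruited throughout, but in changing proportions, so phase is associated with treatment unless the analysis conditions on it.

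At stake is the two-sided 5% error control claimed in SAP 12.0 and 12.2. As written, it depends on there being no period effect, and nothing in the plan tests that.

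**Working it through.** **1. The plan's own power.** Inputs from SAP 8.1.2 and Appendix 7: 31 and 49 subjects, difference 5.034 − 3 = 2.034, SD 2.7, two-sided alpha 0.05. The method is noncentral t power with each arm size multiplied by the Wilcoxon efficiency 3/π:

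- Effective sizes: 31 × 3/π = 29.60 and 49 × 3/π = 46.79.
- Noncentrality: 2.034 / (2.7 × √(1/29.60 + 1/46.79)) = 2.034 / 0.634 = 3.21.
- Power: 88.6% (87.6% with a difference of 2.0). The SAP states 88%.
- With 25% dropout (24 vs 37): 78.8% (77.5% with 2.0). The SAP states 78%.

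The stated power is reproduced, and it counts all 31 placebo subjects.

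**2. Split by phase.** These are expectations from the ratios; actual counts may differ by one or two.

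| | 2:1 phase (17) | 1:2:1 phase (98) | Used below |
|---|---|---|---|
| Placebo | 17/3 = 5.7 | 98/4 = 24.5 | 6 + 25 = 31 |
| Lower dose | 17 × 2/3 = 11.3 | 98/4 = 24.5 | 11 + 24 = 35 |
| Higher dose | 0 | 98/2 = 49 | 49 |

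Lower:placebo allocation moves from 2:1 to 1:1, and pooled active:placebo from 2:1 to 3:1.

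**3. Share of a phase difference that enters each contrast.** Let D be the early minus later mean rate (VOCs/year). The bias in placebo minus active is D times the difference in early fractions:

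- Higher dose: 6/31 − 0 = +0.19D.
- Lower dose: 6/31 − 11/35 = 0.194 − 0.314 = −0.12D.
- Pooled dose: 6/31 − 11/84 = 0.194 − 0.131 = +0.06D.

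**4. Error rate of the higher-dose comparison.** The documents give no value for D, so the shifts are assumptions. Null simulation: 6 early plus 25 later placebo vs 49 higher dose, over-dispersed counts, mean 5/year, SD 2.7 to 4.0, 20,000 trials per case, unstratified asymptotic Wilcoxon test.

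| Early placebo rate | False rejections favouring the higher dose (nominal 2.5%) |
|---|---|
| No difference | about 2.5% |
| 30% higher | about 4–6% |
| 50% higher | about 5–9% |
| Doubled | about 9–13% |
| 30–50% lower | about 0.1–1.2% |

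The last upward row depends on the count model: a gamma-Poisson check in which the spread grows with the mean gave about 15% at SD 2.7. The concurrent-only test stayed near 5% two-sided in every case.

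A separate simulation with normal data (SD 2.7) gave 4.7% at D = 1 and 7.9% at D = 2 for false rejections favouring the higher dose.

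**5. The other two comparisons (normal data, shifts up to 4 VOCs/year).** False rejections favouring the lower dose reach about 5%, at D = −4. Those favouring the pooled dose reach about 4%, at D = +4. With phase as a stratum, two-sided error was 4.8–5.0% in all three comparisons at D = 2 and D = 4.

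**6. Price of conditioning on phase.** For the higher dose, an early stratum has no active subjects and contributes nothing, so stratifying by phase equals using concurrent placebo only:

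- 25 vs 49: noncentrality 2.034 / (2.7 × √(1/23.87 + 1/46.79)) = 2.034 / 0.679 = 3.00, power 84.0% (83.0–84.9% for 24 to 26 placebo).
- With 25% dropout, about 19 vs 37: about 73%.
- Lower dose, same assumed effect: 83.0% falls to 82.2%.
- Pooled dose, same assumed effect: 93.4% falls to 92.8%.

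**The case against.** The case for leaving the rule alone has real content.

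- **The drift is assumed.** No document supplies a figure, and the inflation is marked only for large shifts. Early placebo follow-up of up to 52 weeks overlaps in calendar time with later follow-up, which weakens a pure calendar trend. The actual test stratifies by region and HU use, which would absorb case-mix change along those factors; the simulation does not. This stands: the error rates are conditional illustrations.
- **Only one direction produces false success.** SAP 13.5.2.2 requires a result in favour of the drug. Lower early placebo rates raise two-sided error but cut rejections favouring the drug well below 2.5%. This stands, and those cases are not counted as false-success risk here.
- **The first tipping-point analysis already shifts placebo rates by −50% to +50%.** It shifts the whole arm and cannot separate early from concurrent placebo. It shows general fragility but does not answer this question.
- **Stratifying by phase has a cost.** The 17 early subjects fall into four region-by-HU cells. In simulations with block size 6 and three assumed stratum mixes, at least one early cell held a single arm in 52–73% of trials, losing about one or two subjects on average. This stands, and the fix needs a rule for it.

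A reader might also infer that the change in dose ranges and weight gate makes the early controls non-comparable. The documents do not support that. The change came with Protocol Version 4.0, dated 08 Apr 2021 in SAP 13.5.9, after the higher dose opened, so it falls inside the second phase. It also does not alter what placebo subjects receive.

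**Conclusion.** The point holds as a gap in the plan. Pooling without adjustment makes the error control of the higher-dose comparison depend on an absence of period effects, and no planned analysis examines that. About 19% of the placebo arm is affected, so most controls are concurrent and about 0.19 of any phase difference carries through.

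With no drift there is no bias. Under assumed upward drift of 30–50% in early placebo rates, the chance of a false win is roughly two to three and a half times its nominal 2.5% at the upper end of the ranges, and less at the lower end. The lower-dose and pooled-dose comparisons are affected less, and they are tested only after the higher-dose comparisons succeed.

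A reader might go further and conclude that the primary comparison is biased or its type I error already inflated. The documents do not show this: they report no phase difference. Nor do they require dropping the early placebo subjects from the primary test, which would cost about five power points. This is a cheap improvement to make, not a flaw that invalidates the design. It rests on phase counts expected from the ratios and on the simulation assumptions above.

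**What to change.** Before unblinding, replace the pooling sentence in SAP 13.0 with two rules.

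1. **Higher dose vs placebo as the highest-tolerated-dose comparison.** Keep the pooled primary analysis. Pre-specify a sensitivity analysis of the primary endpoint limited to subjects randomised under the 1:2:1 schedule, and report it next to the primary result. Its power is about 84% instead of 88% without dropout, so it supports the primary test and does not replace it.
2. **Pooled dose vs placebo and lower dose vs placebo.** Add randomisation phase as a stratum. Define phase by randomisation schedule, not by date alone, because a replacement subject inherits the replaced subject's assignment (Protocol 8.6, SAP 8.2) and may enrol after 12 March 2021. State in advance how sparse or empty phase-by-region-by-HU cells are collapsed. Apply the same rule to the primary test if the lower dose becomes the highest tolerated dose.

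Cost: SAP wording, one extra analysis, about one power point or less in the stratified comparisons, and sparse early strata to manage. No new data are needed. Left until after unblinding, a concurrent-placebo check would be post hoc.
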